5.10 Diet/Activity/Other Considerations

5.10.1 Diet

Subjects should maintain a normal diet unless modifications are required to manage an AE such as diarrhea, nausea or vomiting.

5.10.2 Contraception

Pembrolizumab may have adverse effects on a fetus in utero. Furthermore, it is not known if pembrolizumab has transient adverse effects on the composition of sperm. Non-pregnant, non-breast-feeding women may be enrolled if they are willing to use 2 methods of birth control or are considered highly unlikely to conceive. Highly unlikely to conceive is defined as 1) surgically sterilized, or 2) postmenopausal (a woman who is ≥ 45 years of age and has not had menses for greater than 1 year will be considered postmenopausal), or 3) not heterosexually active for the duration of the study. The two birth control methods can be either two barrier methods or a barrier method plus a hormonal method to prevent pregnancy. Subjects should start using birth control from study Visit 1 throughout the study period up to 120 days after the last dose of study therapy.

The following are considered adequate barrier methods of contraception: diaphragm, condom (by the partner), copper intrauterine device, sponge, or spermicide. Appropriate hormonal contraceptives will include any registered and marketed contraceptive agent that contains an estrogen and/or a progestational agent (including oral, subcutaneous, intrauterine, or intramuscular agents).

Subjects should be informed that taking the study medication may involve unknown risks to the fetus (unborn baby) if pregnancy were to occur during the study. In order to participate in the study they must adhere to the contraception requirement (described above) for the duration of the study and during the follow-up period defined in section 8.2.2-Reporting of Pregnancy and Lactation to the Sponsor and to Merck. If there is any question that a subject will not reliably comply with the requirements for contraception, that subject should not be entered into the study.

5.10.3 Use in Pregnancy

If a subject inadvertently becomes pregnant while on treatment with pembrolizumab, the subject will immediately be removed from the study. The site will contact the subject at least monthly and document the subject's status until the pregnancy has been completed or terminated. The outcome of the pregnancy will be reported to the Sponsor and to Merck without delay and within 24 hours to the Sponsor and within 2 working days to Merck if the outcome is a serious adverse experience (e.g., death, abortion, congenital anomaly, or other disabling or life-threatening complication to the mother or newborn).

The study investigator will make every effort to obtain permission to follow the outcome of the pregnancy and report the condition of the fetus or newborn to the Sponsor. If a male subject impregnates his female partner the study personnel at the site must be informed immediately and the pregnancy reported to the Sponsor and to Merck and followed as described above and in Section 8.2.2.

5.10.4 Use in Nursing Women

It is unknown whether pembrolizumab is excreted in human milk. Since many drugs are excreted in human milk, and because of the potential for serious adverse reactions in the nursing infant, subjects who are breast-feeding are not eligible for enrollment.

5.11 Subject Withdrawal/Discontinuation Criteria

Subjects may withdraw consent at any time for any reason or be dropped from the trial at the discretion of the investigator should any untoward effect occur. In addition, a subject may be withdrawn by the investigator or the Sponsor if enrollment into the trial is inappropriate, the trial plan is violated, or for administrative and/or other safety reasons. Specific details regarding discontinuation or withdrawal are provided in Section 8.1.2 – Other Procedures.

A subject must be discontinued from the trial for any of the following reasons:

- The subject or legal representative (such as a parent or legal guardian) withdraws consent.
- Confirmed disease progression
 - Increase in $\geq 25\%$ from best response and/or lowest measurable value in
 - Serum M-component and/or (the absolute increase must be ≥ 0.5 g/dL)
 - Urine M-component and/or (the absolute increase must be ≥ 200 mg/24h)
 - Only in patients without measurable serum and urine M-protein levels: the difference between involved and uninvolved free light chains levels. The absolute increase must be > 10 mg/dl.
 - Bone marrow plasma cell percentage: the absolute % increase must be $\geq 10\%$
 - Definite development of new bone lesions or soft tissue plasmacytomas
 - Development of hypercalcemia (corrected serum calcium > 1 mg/dL higher than the upper limit of normal or > 11 mg/dL) that can be attributed solely to the plasma cell proliferative disorder
 - Rise in serum creatinine by 2 mg/dl or more and/or creatinine clearance > 40 ml/min, that can be attributed solely to the plasma cell proliferative disorder
 - Development of anemia with a hemoglobin 2 g/dl below the lower limit of normal

- Unacceptable adverse experiences as described in Section 5.7.1.2
- Intercurrent illness that prevents further administration of treatment
- Investigator's decision to withdraw the subject
- The subject has a confirmed positive serum pregnancy test
- Noncompliance with trial treatment or procedure requirements
- The subject is lost to follow-up
- Administrative reasons

The End of Treatment and Follow-up visit procedures are listed in Section 7.0 (Study Calendar). After the end of treatment, each subject will be followed for 90 days for adverse event monitoring (serious adverse events will be collected for 90 days after the end of treatment as described in Section 7.0 (study calendar, adverse events/toxicity, footnotes ^{b,j}). Subjects who discontinue for reasons other than progressive disease will have post-treatment follow-up for disease status until disease progression, initiating a non-study cancer treatment, withdrawing consent or becoming lost to follow-up. After documented disease progression each subject will be followed by telephone for overall survival until death, withdrawal of consent, or the end of the study, whichever occurs first.

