5.1.1 Subject Inclusion Criteria

Patients must have histologically confirmed SMM based on the following criteria:

(A) Mayo clinic criteria (patient must have at least 2 risk factors present)¹⁴:

1. Bone marrow core biopsy plasma cell involvement by CD138 immunohistochemistry $\geq 10\%$
2. Monoclonal spike ≥ 3 g/dL
3. Free light chain ratio in serum < 0.125 or > 8 .

*2 of 3 risk factors: intermediate risk for progression at a rate of 51% at 5 years

*3 of 3 risk factors: high risk for progression at a rate of 76% at 5 years

OR

(B) PETHEMA criteria (patient must have at least 1 risk factor present)¹³

1. $\geq 95\%$ abnormal plasma cells/total plasma cells in bone marrow compartment
2. Immunoparesis

*1 of 2 risk factors: intermediate risk for progression at a rate of 46% at 5 years

*2 of 2 risk factors: high risk for progression at a rate of 72% at 5 years

OR

(C) SWOG criteria (patient must have 2 risk factors present or one risk factor if this risk factor if a GEP70 score of > 37.2)¹⁵

1. Monoclonal spike ≥ 3 g/dL
2. Involved free light chain ≥ 25 mg/dL
3. GEP70 risk score > 37.2

* ≥ 2 risk factors: high risk of progression at a rate of 70% at 2 years

* We would also include patients with 1 risk factor as long as this risk factor is GEP70 risk score > 37.2 since patients with this risk factor have an intermediate risk of progression at a rate of 50% at 2 years.

- 5.1.1.1 Creatinine clearance ≥ 50 ml/min. CrCl will be calculated by Cockcroft-Gault method. CrCl (calculated) = $(140 - \text{Age}) \times \text{Mass (in kilograms)} \times [0.85 \text{ if Female}] / 72 \times \text{Serum Creatinine (in mg/dL)}$. If calculated CrCl based on Cockcroft-Gault method is < 50 mL/min, patient will have a 24 hr urine collection to measure CrCl. The measured CrCl must also be ≥ 50 ml/min
- 5.1.1.2 Age ≥ 18 years.
- 5.1.1.3 Eastern Cooperative Oncology Group (ECOG) performance status 0-1
- 5.1.1.4 Absolute neutrophil count (ANC) $\geq 1.0 \times 10^9$ /L, hemoglobin ≥ 10 g/dL and platelet count $\geq 50 \times 10^9$ /L
- 5.1.1.5 Adequate hepatic function with bilirubin < 1.5 x the ULN, and AST and ALT < 3.0 x ULN.
- 5.1.1.6 Subjects must be able to give informed consent
- 5.1.1.7 Female subject of childbearing potential should have a negative urine or serum pregnancy within 72 hours prior to receiving the first dose of study medication. If the urine test is positive or cannot be confirmed as negative, a serum pregnancy test will be required.

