5.1.2 Subject Exclusion Criteria

The subject must be excluded from participating in the trial if the subject has any of the following:

- 5.1.2.1 Evidence of myeloma defining events or biomarkers of malignancy due to underlying plasma cell proliferative disorder meeting at least one of the following¹⁶
 - 1) Hypercalcemia: serum calcium >0.25 mmol/L (>1 mg/dL) higher than the upper limit of normal or > 2.75 mmol/L (> 11 mg/dL)
 - 2) Renal Insufficiency: creatinine clearance < 40 ml/min or serum creatinine > 2 mg/dL
 - 3) Anemia: hemoglobin value <10 g/dL or 2 g/dL < normal reference
 - 4) Bone lesions: one or more osteolytic lesions on skeletal radiography, computerized tomography (CT) or 2-deoxy-2[F-18] fluoro-D-glucose positron emission tomography CT (PET-CT).
 - 5) Clonal bone marrow plasma cell percentage $\geq 60\%$
 - 6) Involved: uninvolved serum free light chain ratio ≥ 100 measured by Freelite assay (The Binding Site Group, Birmingham, UK)
 - 7) >1 focal lesions on MRI studies (each focal lesion must be 5 mm or more in size), if clinically indicated

- 5.1.2.2 Prior or concurrent systemic treatment for SMM.
 - a) Bisphosphonates are permitted.
 - b) Treatment with corticosteroids is not permitted
 - c) Radiotherapy is not permitted.
 - d) Prior treatment for smoldering multiple myeloma with chemotherapy agents approved for the treatment of multiple myeloma is not permitted.
- 5.1.2.3 Plasma cell leukemia
- 5.1.2.4 Pregnant or lactating females. Because there is a potential risk for adverse events in nursing infants secondary to treatment of the mother with pembrolizumab, breastfeeding should be discontinued if the mother is treated with pembrolizumab. These potential risks may also apply to other agents used in this study.
- 5.1.2.5 Has a diagnosis of immunodeficiency or is receiving systemic steroid therapy or any other form of immunosuppressive therapy within 7 days prior to the first dose of trial treatment.
- 5.1.2.6 Has a known history of active TB (Bacillus Tuberculosis)
- 5.1.2.7 Hypersensitivity to pembrolizumab or any of its excipients.
- 5.1.2.8 Has had a prior anti-cancer monoclonal antibody (mAb) within 4 weeks prior to study Day 1 or who has not recovered (i.e., \leq Grade 1 or at baseline) from adverse events due to agents administered more than 4 weeks earlier.

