5.4 Biospecimen collection

5.4.1 Correlative Studies

5.4.1.1 Bone Marrow

Sampling Time Points of Bone Marrow correlative studies (see Table 1)

- a) Baseline
- b) Post cycle 8
- c) Post cycle 24 (in patients receiving an additional 16 cycles of therapy only)
- d) At progression
- e) End of Study

Table 1	Baseline	Post Cycle 8 /end of study	Post Cycle 24 /end of study	Progression of Disease
Pathology/immuno- histochemistry	X	X	X	X
Multiparametric Flow Cytometry	X	X	X	X
FISH/Cytogenetics	X	X	X	X
Gene expression profiling	X			X
VDJ sequencing	X	X	X	X
Immune studies	X	X	X	X
Cytometry time of flight (CyTOF)	X	X	X	X
Whole exome sequencing	X			X
Storage	X	X	X	X

- Correlative studies associated with bone marrow specimen will be performed and related to clinical outcome if the results of the study indicate a clinical or translational rationale for analyzing the samples. Such studies may include but are not limited to the following:
 - Pathology/Immunohistochemistry: Bone marrow biopsy and aspirate will be sent to the Department of Pathology at MD Anderson Cancer Center. Immunohistochemical staining will be performed. Plasma cell burden will be assessed using immunohistochemistry markers such as CD138, light chains, CD56 etc.
 - Minimal Residual Disease:
 - Flow cytometry: Immunophenotyping of aberrant plasma cells by flow cytometry currently involves, but is not limited to, the use of the following reagents: CD138, CD19, CD45, CD38, and CD56. Characteristic changes in immunophenotypically abnormal plasma cells (CD138 positive) include but are not limited to absent CD19 and CD45, decreased CD38, and increased CD56. These studies will be performed following the Euroflow method.
 - Bone marrow, blood and urine samples, and associated clinical lab data will be sent to Adaptive Biotechnologies (Seattle, Washington) for deep sequencing of the VDJ sequence. Samples and data will be submitted to Adaptive Biotechnologies in an anonymized and de-identified manner.
 - FISH and cytogenetics: Interphase FISH/cytogenetics will be performed on patients enrolled in this protocol under the direction of the Molecular Diagnostics Core Laboratory of the Department of Pathology at MD Anderson Cancer Center

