- Negative immunofixation on the serum and urine and disappearance of any soft tissue plasmacytomas and $\leq 5\%$ plasma cells in bone marrow

c) Very Good Partial Response (VGPR)

- Serum and urine M-protein detectable by immunofixation but not on electrophoresis or 90% or greater reduction in serum M-protein plus urine M-protein level $< 100\text{mg}$ per 24h. If the serum and urine M-protein are unmeasurable, a $\geq 90\%$ decrease in the difference between involved and uninvolved FLC levels is required in place of the M-protein criteria.

d) Partial Response (PR)

- $\geq 50\%$ reduction in M protein and reduction in 24-h urinary M-protein by $\geq 90\%$ or to $< 200\text{ mg}$ per 24h. If the serum and urine M-protein are unmeasurable, a $\geq 50\%$ difference between involved and uninvolved FLC levels is required in place of the M-protein criteria

e) Minor Response (MR)

- $\geq 25\%$ but $\leq 49\%$ reduction of serum M protein and reduction in 24-hour urine M-protein by 50%-89%. In addition to this, if present at baseline, 25%-49% reduction in the size of soft tissue plasmacytomas is also required. No increase in size or number of lytic bone lesions (development of compression fracture does not exclude response)

f) Stable Disease (SD)

- Not meeting criteria for CR, VGPR, PR, MR or progressive disease. All categories also require no known evidence of progressive or new bone lesions if radiographic studies were performed. Radiographic studies are not required to satisfy these response requirements.

g) Progressive disease (PD)

- Requires any one or more of the following:
 - Increase of $\geq 25\%$ of best response and/or lowest measurable value in:
 - Serum M-component and/or (absolute increase must be $\geq 0.5\text{ g/dl}$.
The serum M-component increases of $\geq 1\text{ gm/dl}$ are sufficient to define

relapse if starting M-component is ≥ 5 gm/dl.

- Urine M-component and/or (the absolute increase must be ≥ 200 mg/24h
- Only in patients without measureable serum and urine M-protein levels: the difference between involved and uninvolved FLC levels. The absolute increase must be >10 mg/dl.
- Bone marrow plasma cell percentage: the absolute % must be $\geq 10\%$
- Definite development of new bone lesions or soft tissue plasmacytomas or definite increase in size of existing bone lesions or soft tissue plasmacytomas
- Development of that can be attributed solely to the plasma cell proliferative disorder

h) Relapse from CR:

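### Section 5.11 reverses the renal inequality in its progression-removal list (clearance > 40 instead of < 40 ml/min), and its marrow rule differs from the one in 6.2.2(g).

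*Combined protocol and SAP*

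**What the plan says.** Section 5.11 introduces its list with "A subject must be discontinued from the trial for any of the following reasons", and confirmed progression is one of the reasons. Its renal item is an increase of "serum creatinine by 2 mg/dl or more and/or creatinine clearance > 40 ml/min, that can be attributed solely to the plasma cell proliferative disorder".

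Two other places set renal limits. Inclusion 5.1.1.1 requires "Creatinine clearance ≥ 50 ml/min" and states that "CrCl will be calculated by Cockcroft-Gault method"; a calculated value below 50 leads to a 24-hour urine measurement, which must itself be at least 50. Exclusion 5.1.2.1(2) describes the renal myeloma-defining event as "Renal Insufficiency: creatinine clearance < 40 ml/min or serum creatinine > 2 mg/dL".

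For marrow, 5.11 reads "Bone marrow plasma cell percentage: the absolute % increase must be" at least 10%. Section 6.2.2(g), the response-criteria definition of progressive disease, reads "Bone marrow plasma cell percentage: the absolute % must be" at least 10%. In both sections the marrow line sits under a required relative rise of at least 25% from the best or lowest value.

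**The concern.** The 5.11 list tells a site when a patient must leave the trial. A clearance above 40 cannot signal renal damage from myeloma; a clearance below 40 can, and the protocol says so in its exclusions. With the sign reversed, the clearance limb does not do its job. The remaining limb, an absolute creatinine rise of 2 mg/dl, is a much coarser signal in a patient who starts with modest clearance.

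The marrow lines differ by one word, but that word changes the rule from a level to an increase. The same patient can have progressive disease under the response criteria and no marrow reason for removal under 5.11. The protocol does not say which rule governs. At stake is a clear, reproducible removal decision in a 16-patient trial.

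**Working it through.** **Renal sign.** Inputs: printed limit > 40 (5.11), myeloma event < 40 (5.1.2.1(2)), entry floor 50 (5.1.1.1), all in ml/min.

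| Clearance | Printed: > 40 | Corrected: < 40 |
|---|---|---|
| 120 | met | not met |
| 50 (entry floor) | met | not met |
| 39 | not met | met |
| 30 | not met | met |

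The sign is unlikely to come from reading the PDF. Both inequality signs appear correctly in 5.1.2.1(2), and the calcium item in the same 5.11 list has the right direction.

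**How late the creatinine limb can be (illustration).** Assumption: on-study clearance is calculated by Cockcroft-Gault with age, weight and sex fixed, so clearance is proportional to 1/creatinine. Let C0 and S0 be clearance and creatinine at entry.

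- Rise in creatinine at which clearance reaches 40: S0 × (C0/40 − 1).
- Clearance when creatinine has risen by 2: C0 × S0/(S0 + 2).

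For C0 = 50 and S0 = 1.0: the rise is 1.0 × (50/40 − 1) = 0.25 mg/dl, and clearance at the 2 mg/dl rise is 50 × 1.0/3.0 = 16.7 ml/min.

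The documents give no distribution of entry creatinine, so a range at C0 = 50 is shown:

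| S0 (mg/dl, assumed) | Rise to reach 40 | Clearance at +2 mg/dl |
|---|---|---|
| 0.8 | 0.20 | 14.3 |
| 1.0 | 0.25 | 16.7 |
| 2.0 | 0.50 | 25.0 |

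The limb is not late for everyone. It is met no later than clearance 40 when C0 ≥ 40 × (1 + 2/S0), which at S0 = 1.0 is 120 ml/min.

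**Marrow.** For a reference value n (in %), progression requires:

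- 6.2.2(g): the larger of 1.25n and 10.
- 5.11: the larger of 1.25n and n + 10.

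| n | 6.2.2(g) | 5.11 | Gap (points) |
|---|---|---|---|
| 8 | 10 | 18 | 8 |
| 10 | 12.5 | 20 | 7.5 |
| 20 | 25 | 30 | 5 |
| 30 | 37.5 | 40 | 2.5 |
| 40 | 50 | 50 | 0 |

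From n = 40 upward, 0.25n is at least 10, so the rules agree. The gap is widest at n = 8. A marrow going from 20% to 25% rises by 25% in relative terms and 5 points in absolute terms: it is progression under 6.2.2(g) and not under 5.11.

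**Where the marrow difference can bite.** Apart from baseline, progression and end of study, section 5.4.1.1 schedules marrows only after cycle 8 and "Post cycle 24 (in patients receiving an additional 16 cycles of therapy only"). Cycle 24 ends treatment, and under 2.1 the additional 16 cycles are for patients with at least a minor response after cycle 8. The mismatch therefore changes on-treatment removal mainly for a patient with at least a minor response at cycle 8 whose marrow alone worsens.

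**The case against.** The strongest reply is that the renal slip corrects itself. The item must be attributable solely to the plasma cell disorder, and an adequate clearance cannot be. A reader might infer that the text obliges sites to remove everyone at entry; the attribution clause rules that out. A clinician would probably see the error, and 5.11 separately allows withdrawal by investigator decision. This stands, and it is why the point is minor. It does not make a reversed threshold in a mandatory list correct.

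A second reply concerns the arithmetic. A reader might go further and say that the creatinine limb is late for every entry clearance from 50 to below 80. The documents do not support that. Cockcroft-Gault is specified for eligibility only, and the Study Calendar lists an eGFR among routine tests. The 2 mg/dl creatinine limit in 5.1.2.1(2) covers only renal disease due to the plasma cell disorder, so it is not a general ceiling. At an entry creatinine of 2.5, for example, the limb is in time from a clearance of 40 × (1 + 2/2.5) = 72. The figures above are illustrations.

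A third reply is that the marrow difference is a dropped word with small reach. The reach is indeed small. But nothing in the documents shows which section lost or gained the word.

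**Conclusion.** Both discrepancies are real. The renal inequality in 5.11 contradicts the protocol's own definition of the renal event. The marrow rules in 5.11 and 6.2.2(g) disagree by up to 8 points, for reference values below 40%. Severity is minor. How many of the 16 patients would be affected cannot be derived from the documents. The renal sign error rests on the text alone; only its illustrated delay depends on assumed on-study Cockcroft-Gault and assumed entry creatinine values.

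Three stronger inferences should not be drawn.

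- No effect on the primary endpoint, the Simon design, TTP or PFS is shown. Response is defined in 6.2.2, and 6.2.4 and 6.2.5 define PFS and TTP by progression to multiple myeloma.
- Nothing firm follows about lost follow-up after removal. Section 5.11 specifies telephone contact for survival after progression, while the Study Calendar (footnote i) and 8.1.2.1.1 also provide for tests as indicated and clinic visits.
- No view is taken on renal, calcium or anaemia items in 6.2.2(g), because a bullet there is incomplete in the text available.

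**What to change.** In 5.11, change the clearance limb to creatinine clearance < 40 ml/min, to match 5.1.2.1(2).

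For marrow, ask the sponsor whether a level of at least 10% or an absolute increase of at least 10 points is intended, and print that one rule in both 5.11 and 6.2.2(g). The documents give no ground for preferring either.

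The cost is protocol wording, with no added tests, visits or patients. The marrow choice is still a clinical decision: from a reference of 20%, it places the threshold at 25% or at 30%.

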Pneumonitis	2	Toxicity resolves to Grade 0-1	Toxicity does not resolve within 12 weeks of last dose or inability to reduce corticosteroid to 10 mg or less of prednisone or equivalent per day within 12 weeks.
	3-4	Permanently discontinue	Permanently discontinue
Renal Failure or Nephritis	2	Toxicity resolves to Grade 0-1	Toxicity does not resolve within 12 weeks of last dose or inability to reduce corticosteroid to 10 mg or less of prednisone or equivalent per day within 12 weeks.
	3-4	Permanently discontinue	Permanently discontinue
All Other Drug-Related Toxicity ²	3 or Severe	Toxicity resolves to Grade 0-1	Toxicity does not resolve within 12 weeks of last dose or inability to reduce corticosteroid to 10 mg or less of prednisone or equivalent per day within 12 weeks.
	4	Permanently discontinue	Permanently discontinue
Note: Permanently discontinue for any severe or Grade 3 drug-related AE that recurs or any life-threatening event.			
¹ For patients with liver metastasis who begin treatment with Grade 2 AST or ALT, if AST or ALT increases by greater than or equal to 50% relative to baseline and lasts for at least 1 week then patients should be discontinued.			
² Patients with intolerable or persistent Grade 2 drug-related AE may hold study medication at physician discretion. Permanently discontinue study drug for persistent Grade 2 adverse reactions for which treatment with study drug has been held, that do not recover to Grade 0-1 within 12 weeks of the last dose.			

Dosing interruptions are permitted in the case of medical / surgical events or logistical reasons not related to study therapy (e.g., elective surgery, unrelated medical events, patient vacation, and/or holidays). Subjects should be placed back on study therapy within 3 weeks of the scheduled interruption, unless otherwise discussed with the Sponsor. The reason for interruption should be documented in the patient's study record.

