- g. Baseline bone marrow aspiration and biopsy will be sent to Department of Pathology, flow cytometry, FISH/cytogenetics, multiple myeloma tissue bank, gene expression profiling, whole exome sequencing, VDJ sequencing and storage.
- h. Bone marrow aspirate and biopsy can be performed +/- 21 days of intended cycle day. Bone marrow aspirate and biopsy will be sent to Department of Pathology, flow cytometry, FISH/cytogenetics, gene expression profiling, VDJ sequencing and storage.
- i. At minimum, follow-up will be every 6-12 months until progression of disease, institution of alternative therapy, or death. Patients may be followed at more frequent time intervals if clinically indicated, ie following post-therapy toxicity. Patients who have progressive disease while on study will be followed with restaging scans and laboratory tests as clinically indicated. Patients who are taken off treatment will continue to be followed for survival by phone or clinic visit.
- j. Variations of +/- 14 days of scheduled visits are permitted.
- k. Variations of +/- 3 days of scheduled visits are permitted.
- l. Peripheral blood sample only.
- m. If clinically indicated
- n. All concomitant medications received within 28 days before the first dose of trial treatment and 30 days after the last dose of trial treatment should be recorded in the medical record.

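### The anemia item under confirmed progression in section 5.11 omits attribution to the plasma cell disorder, so anemia of another cause would literally require discontinuation as progressed (minor)

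*Combined protocol and SAP*

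**What the plan says.** Section 5.11 lists the reasons for which a subject has to leave the trial. One is confirmed disease progression, with sub-items stating what counts. Three of these are laboratory events that illnesses other than myeloma can also produce: hypercalcemia, renal decline and anemia. The first two each end with the condition "that can be attributed solely to the plasma cell proliferative disorder". The anemia item, immediately below, is only "Development of anemia with a hemoglobin 2 g/dl below the lower limit of normal".

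At entry, exclusion criterion 5.1.2.1 opens with "Evidence of myeloma defining events or biomarkers of malignancy due to underlying plasma cell proliferative disorder", and that lead-in governs every item in its list, anemia included. Inclusion criterion 5.1.1.4 separately asks for "hemoglobin ≥ 10 g/dL and platelet count" above a stated level.

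Table 3 in section 5.7.1.2 has a row for "All Other Drug-Related Toxicity". It holds treatment for Grade 3 or severe events, allows restart on recovery to Grade 0-1, and stops treatment permanently for Grade 4.

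After discontinuation, section 5.11 separates two groups. For the first: "Subjects who discontinue for reasons other than progressive disease will have post-treatment follow-up for disease status until disease progression". For the second: "After documented disease progression each subject will be followed by telephone for overall survival until death". Footnote i of the Study Calendar (section 7.0) adds: "At minimum, follow-up will be every 6-12 months until progression of disease, institution of alternative therapy, or death"; for patients who have progressed it provides scans and laboratory tests only when clinically indicated. Section 8.1.2.1.1, by contrast, has progressed patients seen in clinic according to the calendar, whose follow-up column includes myeloma tests.

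Time to progression (TTP) at 30 months from study entry is a secondary objective (section 3.2). Section 6.2.5 defines it as the time to progression to multiple myeloma.

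**The concern.** The protocol requires attribution for anemia at entry, and for calcium and renal events on study, but not for anemia on study. The M-protein, marrow and bone or plasmacytoma items also carry no attribution wording, but they are specific to the disease and do not need it. Anemia is not specific: bleeding, iron deficiency and the study drug can all lower hemoglobin.

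Two things are at stake. First, a patient with drug-related anemia could be removed permanently where Table 3 might have allowed a hold and restart. Second, a patient whose disease has not progressed would be moved out of disease-status follow-up. Discontinuation under this item is not itself a TTP event, because TTP needs progression to multiple myeloma. But the date of a later, true progression could go unrecorded if no visit is scheduled to detect it.

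**Working it through.** The plan gives no figure on this point, so the check is mainly a comparison of texts, followed by what one affected patient could lose.

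**Attribution requirement, rule by rule**

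| Rule | Attribution to plasma cell disorder required? |
|---|---|
| 5.1.2.1, anemia at entry | Yes, through the lead-in |
| 5.11, hypercalcemia | Yes, in the item |
| 5.11, renal | Yes, in the item |
| 5.11, anemia | No |

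The progression definition in 6.2.2(g) cannot settle the matter. Its organ-event line is partly unreadable, so nothing is inferred from it either way.

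**Follow-up window at risk**

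Inputs: 21-day cycles (section 2.1); TTP at 30 months from study entry (section 3.2), with entry taken here as treatment start; minimum visits every 6-12 months (section 7.0, footnote i); 1 month = 30.44 days.

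Remaining window = 30 − (day of discontinuation / 30.44). Minimum-schedule visits run from floor(remaining / 12) to floor(remaining / 6).

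| Discontinued at | Day | Months elapsed | Months left | Visits, 12-monthly to 6-monthly |
|---|---|---|---|---|
| Day 1 of Cycle 2 | 21 | 0.69 | 29.31 | 2 to 4 |
| End of Cycle 8 | 8 × 21 = 168 | 5.52 | 24.48 | 2 to 4 |
| End of Cycle 24 | 24 × 21 = 504 | 16.56 | 13.44 | 1 to 2 |

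Once the patient is labeled as progressed, none of these visits is guaranteed under the follow-up paragraph of 5.11 or footnote i. Under 8.1.2.1.1 clinic visits continue and the loss may be 0. In the last row the 24-cycle maximum has been reached, so only follow-up is at risk, not treatment.

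**Overlap with the entry criteria**

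The 5.11 threshold is the lower limit of normal (LLN) minus 2 g/dL. The entry floor is 10 g/dL. The documents give no LLN, so the values below are assumptions.

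| Assumed LLN (g/dL) | 5.11 threshold (g/dL) | Band from 10 to threshold | Width (g/dL) |
|---|---|---|---|
| 12 | 10 | 10 only | 0 |
| 13 | 11 | 10-11 | 1 |
| 14 | 12 | 10-12 | 2 |

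Within the band, anemia of another cause does not bar entry, yet the same hemoglobin first reached on study would meet the 5.11 item. Because that item speaks of anemia developing, a patient already in the band at entry does not trigger it simply by staying there.

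**The case against.** The strongest reply is that the heading already supplies the meaning. The reason for discontinuation is confirmed progression of the disease, and iron deficiency is not progression. The adverse event sections point the same way: section 8.2 separates progression of the cancer from adverse events, and Table 5 has a qualified physician judge the cause of every adverse event, with underlying disease as one of the explanations to consider. Harm therefore needs an investigator to apply the item against its evident purpose.

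This makes the literal reading less likely, but it does not amend 5.11. If the heading were enough, the attribution phrase on the calcium and renal items would be redundant; its presence there suggests that its absence from the anemia item means something.

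Other parts of the reply stand and limit the point:

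- The follow-up gap comes from the inconsistency among 5.11, footnote i and 8.1.2.1.1. It also affects patients discontinued under another 5.11 item before reaching multiple myeloma. The missing phrase adds patients with no progression at all. The months and visit counts above describe the exposure of one such patient; they do not measure how often the wording does harm.
- The Table 3 conflict is conditional. The documents do not say which toxicity grade corresponds to the 5.11 hemoglobin threshold.
- The entry overlap depends on the assumed LLN and shrinks to a single value at 12 g/dL.

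**Conclusion.** The concern holds and is minor. Section 5.11 as written gives the wrong result for anemia not caused by the plasma cell disorder: mandatory discontinuation with a progression label. For one affected patient, up to 29.3 months of the TTP window and up to 4 minimum-schedule visits could be left unsecured. The loss may be nil if 8.1.2.1.1 is the rule applied. How often this would happen cannot be derived, because the documents give no anemia rate and the harm also requires a literal reading by the investigator. No effect is claimed on the primary endpoint or on the accept/reject rule of the two-stage design. The figures assume that study entry coincides with treatment start.

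**What to change.** In section 5.11, extend the anemia item with the words already used in the two items above it: "that can be attributed solely to the plasma cell proliferative disorder". State that anemia of any other cause is handled under the adverse event rules and Table 3, and that a patient who stops treatment for it stays in disease-status follow-up like anyone else who stops for a reason other than progression.

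The cost is one phrase in the criterion plus that clarification. No new tests are needed, since a blood count is already taken on Day 1 of every cycle (section 5.6.1.2), and the two-stage design's sample sizes and cut-offs are unchanged.
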